13.1.2 Sensitivity Analysis

The following sensitivity analyses of the primary efficacy endpoint are planned to account for intercurrent events.

13.1.2.1 Pattern-Mixture Models Assuming Missing Not At Random (MNAR) Using Multiple Imputation (MI)

MMRM assumes data are MAR, which is a reasonable assumption in longitudinal clinical trials. However, the possibility of missing not at random (MNAR) data can never be ruled out. In order to further evaluate robustness of the primary results to deviations from MAR assumptions, additional sensitivity analyses may be conducted.

Placebo Based Imputation Methods

Similar to "Standard" multiple imputations, except parameters for imputation model obtained from only the placebo (control) group. Missing data for both placebo and pimavanserin high and low dose groups are imputed based on the imputation model derived from placebo data within each stage. If pimavanserin high and/or low doses improved outcomes prior to dropout, this benefit is carried into subsequent imputed values, but will diminish over time in accordance with the correlation structure.

13.1.2.2 Tipping Point Analyses

Sensitivity analyses based on pattern-mixture model (PMM) using MI will be performed in order to explore data missing mechanisms of MNAR and investigate the response profile of dropout reasons for the following scenarios:

- 1) Dropout reason due to Adverse Event (AE) as MNAR
- 2) Dropout reasons due to AE, lack of efficacy (LOE), COVID-19, use of prohibited medication as MNAR
- 3) All dropouts not due to COVID-19 as MNAR
- 4) All dropouts as MNAR

This sensitivity analysis will be implemented for Full Analysis Set using delta adjustment imputation. This MNAR sensitivity analysis is to departure from MAR assumption by progressively increasing the delta until conclusion from the primary analysis is overturned. The delta is 0%, 5%, 10%, 15%, ..., 100% of the observed treatment difference between a pimavanserin high dose and placebo, pimavanserin low dose and placebo, from the primary analysis of MMRM model until conclusion of the primary analysis is overturned. When delta = 0 the missing data are assumed to be MAR. When delta > 0, the missing data are assumed to be MNAR.

- 1) Using Monte Carlo Markov Chain (MCMC) methodology from PROC MI to impute the intermittent missing data to a monotone missing pattern
- 2) Using a standard MAR-based multiple imputation approach from PROC MI to impute the monotone missingness data
- 3) For subjects in the pimavanserin group with a dropout reason due to AE, LOE, subject withdraw consent, COVID-19, use of prohibited medication, a delta will be added for all the values after the dropout time
- 4) Using MMRM model in the primary analysis to analyze the completed data using PROC MIXED on the multiple imputed data
- 5) Obtaining the overall results using PROC MIANALYZE.

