2 EFFICACY ANALYSES

Section 12.4 Multiple Comparisons / Multiplicity (Page 27):

In response to the FDA's comments, the hierarchical testing procedure has been reverted to the testing procedures outlined in the previous version of the SAP, dated December 22, 2022, which is consistent with the protocol.

A hierarchical testing procedure will be used to control the Type I error rate across the two treatment comparisons (pimavanserin high dose vs. placebo and pimavanserin low dose vs. placebo) for the primary endpoint. The hypotheses testing will be conducted in sequential order: 1. pimavanserin high dose versus placebo, 2. pimavanserin low dose versus placebo. If the first comparison fails to reach statistical significance at the 2-sided 0.05 level, the subsequent comparison will be declared as not statistically significant regardless of the associated nominal p-value. The study-wise Type I error rate will be maintained at the significance level of 0.05.

Section 13.1.2.2 Tipping Point Analyses (Page 32):

In response to the FDA's comments, the tipping point analyses have been updated to remove the limitation on the delta value, allowing it to exceed 100% until the conclusion of the primary analysis is overturned.

This sensitivity analysis of the tipping point analysis will be implemented for Full Analysis Set using delta adjustment imputation. This MNAR (missing not at random) sensitivity analysis is to departure from MAR (missing at random) assumption by progressively increasing the delta until conclusion from the primary analysis is overturned. The delta value is 0% to 100%, 200%,.... in 5% increments of the observed treatment difference between a pimavanserin high dose and placebo, pimavanserin low dose and placebo, from the primary analysis of MMRM (mixed model for repeated measures) model until conclusion of the primary analysis is overturned.

Signature Page for ACP-103-069 Statistical Analysis Plan Addendum

Approval w eSig Task	PPDPPDPPD
	14-Oct-2024 17:46:04 GMT+0000
Approval w eSig Task	PPD 1cs 14-Oct-2024 17:46:43 GMT+0000
Approval w eSig Task	PPD s 14-Oct-2024 18:47:45 GMT+0000

Signature Page for ACP-103-069 Statistical Analysis Plan Addendum

STATISTICAL ANALYSIS PLAN

Protocol No.:	ACP-103-069
Protocol Title:	A Phase 2, Randomized, Double-blind, Placebo-controlled Study to Evaluate the Efficacy and Safety of Pimavanserin for the Treatment of Irritability Associated With Autism Spectrum Disorder
Drug:	Pimavanserin

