3.5 Determination of Sample Size

The planned sample size is a total of 228 subjects for both age groups combined (76 subjects randomized to each of the three treatment groups of equal sample sizes: pimavanserin high dose group, pimavanserin low dose group, and the placebo group). The total study sample size will be comprised of at least 35% (80) subjects in the younger age group (5- through 12-year-olds).

Assuming the true difference in the mean change in the ABC-Irritability (ABC-I) subscale score from Baseline at Week 6 is 5 points between each pimavanserin dose group and the placebo group, and assuming the common standard deviation is 10 points, 64 evaluable subjects per treatment group will provide 80% power to detect the difference between either pimavanserin dose group and the placebo group at a significance level of 0.05, using a 2-sided t-test. Adjusting for a potential discontinuation rate of up to 15%, approximately 76 subjects per treatment group, or 228 total subjects, will be randomized.

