13.1.2.3 Sensitivity Analysis Using Randomized Analysis Set

This sensitivity analysis using MI assuming MAR will be performed using the Randomized Analysis Set.

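### The tipping-point analysis is confined to the Full Analysis Set, so its all-dropouts scenario cannot include randomised children with no usable post-baseline ABC-I, and no other MNAR analysis covers them

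*SAP*

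**What the plan says.** SAP 13.1.2.2 lists four MNAR scenarios, the widest being "All dropouts as MNAR". On the population it states: "This sensitivity analysis will be implemented for Full Analysis Set using delta adjustment imputation". The addendum (section 2, update to 13.1.2.2) lifts the 100% limit on delta in response to FDA comments but leaves the population alone: "This sensitivity analysis of the tipping point analysis will be implemented for Full Analysis Set using delta adjustment imputation".

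Under SAP section 4, the FAS requires at least one dose, a baseline ABC-I and at least one post-baseline ABC-I. SAP section 12 places all efficacy analyses on this set. That includes the placebo-based imputation of 13.1.2.1, which names no other population and comes under analyses that the SAP says may be conducted.

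The one analysis on a wider set is 13.1.2.3: "This sensitivity analysis using MI assuming MAR will be performed using the Randomized Analysis Set".

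Step 3 of 13.1.2.2 adds delta only in the pimavanserin group, and only for dropout due to adverse event, lack of efficacy, withdrawn consent, COVID-19 or prohibited medication.

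**The concern.** A tipping-point analysis asks how bad the unseen outcomes would have to be before the primary conclusion fails. Scenario 4 is presented as the version in which no dropout is given the benefit of MAR. A child with no usable post-baseline ABC-I is the one about whom least is known, and the population rule removes that child before any delta is applied. The analysis that brings the child back assumes MAR, which is the assumption under test. So no planned analysis puts these children under an MNAR assumption.

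At stake is how the tipping delta is read. Delta is added on the pimavanserin side only. If some pimavanserin dropouts are absent, a smaller share of the arm is shifted, and a larger delta is needed to overturn a significant result. The figure will be read closely, since its range was extended after regulatory comment.

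**Working it through.** **Design figures.** SAP 3.5 assumes that the difference "is 5 points between each pimavanserin dose group and the placebo group", "assuming the common standard deviation is 10 points", and testing "at a significance level of 0.05, using a 2-sided t-test". It concludes that "64 evaluable subjects per treatment group will provide 80% power". This reproduces: the noncentral t power is 80.1% at 64 per arm (79.5% at 63). Then 64 / 0.85 = 75.3, rounded up to 76 per arm, and 3 × 76 = 228. A 15% dropout rate is 0.15 × 76 = 11.4 children per arm, bracketed below by 11 and 12.

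**Who is outside the FAS.** In SAP 5.3.2 the baseline window ends at Day 1 and the Week 1 window runs from Day 2 to Day 11. SAP 5.3.3 counts early-termination (ET) assessments towards these windows, so a child who stops on Day 3 and gives an ET rating stays in the FAS. The gap is therefore limited to children with no usable rating from Day 2 onward. It is not empty by construction:

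- The schedule of events omits the ET visit after withdrawal of consent to all parts of the study.
- SAP 13.1.1 expects no ET evaluation after loss to follow-up or death.
- SAP 5.2.1 sets the subscale score to missing if any item is missing.

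**Effect on the tipping delta.** Let D be the dropouts in the pimavanserin arm and k those with no post-baseline ABC-I. The share shifted is D/76 on all randomised subjects and (D − k)/(76 − k) on the FAS. To first order:

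tipping delta = (observed difference − t × SE) / share shifted.

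Assumptions: observed difference 5 (the design value); SE = 10 × √(2/64) = 1.768, the same for both populations; t = 1.979 on 126 degrees of freedom; every dropout receives delta; extra imputation variance ignored. The numerator is 5 − 1.979 × 1.768 = 1.50 points.

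| D | k | Share shifted, FAS | Tipping delta, FAS | Tipping delta, all randomised | Excess |
|---|---|---|---|---|---|
| 12 | 0 | 12/76 | 9.5 | 9.5 | 0% |
| 12 | 1 | 11/75 | 10.2 | 9.5 | 8% |
| 12 | 2 | 10/74 | 11.1 | 9.5 | 17% |
| 12 | 3 | 9/73 | 12.2 | 9.5 | 28% |
| 11 | 1 | 10/75 | 11.3 | 10.4 | 9% |
| 11 | 3 | 8/73 | 13.7 | 10.4 | 32% |

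The numerator cancels in the ratio, so the percentage excess does not depend on the observed difference in this approximation.

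**Check by simulation.** A simplified model was used: one endpoint, a baseline covariate, 12 dropouts in each arm of 76, multiple imputation with Rubin's rules, and 60 runs per setting, keeping the 53 to 57 runs that were significant before any delta. The median ratio of the FAS delta to the all-randomised delta was:

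- 1.07 with one child omitted per arm;
- 1.23 with three omitted per arm;
- 1.24 with three omitted on pimavanserin only;
- 1.00 with three omitted on placebo only (FAS value larger in 29% of runs, smaller in 38%).

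The closed form therefore runs a little high, and the direction depends on omissions in the pimavanserin arm. This is not the full six-visit MMRM.

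**Scenario 4 inside the FAS.** Protocol 4.5 lists discontinuation reasons that step 3 does not, among them loss to follow-up and physician decision. Read literally, step 3 leaves those dropouts unshifted even within the FAS. That conflicts with the scenario's label and also raises the tipping delta.

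**The case against.** The best defence is that the tipping point tests the MAR assumption of the primary MMRM, which is itself on the FAS, and scales delta to that model's estimate. Keeping the same population changes one assumption at a time, and 13.1.2.3 examines the population question separately. This is a fair reason to keep the FAS run. It does not supply an MNAR analysis for the omitted children, nor does it square with a scenario described as covering all dropouts.

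Second, SAP section 6 already plans FAS counts by treatment group and a listing of exclusions with reasons. Readers will see how many are missing and from which arm. That discloses the gap but does not test it.

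Third, the practical effect may be small. ET ratings may capture most early leavers. In the illustration with 12 dropouts, delta is 190% of the observed difference on all randomised subjects and 205% to 244% on the FAS with one to three omitted, which would hardly change a reader's view. This stands, and it makes the point an improvement to the plan, not a defect in the primary analysis.

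A reader might go further and infer that the reported tipping delta is bound to be too large, or that every early dropout is left out. The documents support neither. They give no count of omitted children, ET ratings keep many early leavers in, and omissions confined to placebo leave the delta essentially unchanged.

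**Conclusion.** The omission follows directly from the FAS definition, and the addendum does not cure it. Randomised children with no usable ABC-I from Day 2 onward are outside all four tipping-point scenarios, and the only analysis that includes them assumes MAR.

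The consequence is conditional. It needs a significant primary comparison and at least one omitted child in the pimavanserin arm compared. Under the stated assumptions, the tipping delta is then overstated by about 8 to 9% for one such child (7% in simulation) and by about 23 to 32% for three, taking simulation and closed form together. With none omitted the excess is zero. The numbers omitted are assumed, so these percentages are illustrations and not forecasts. The mismatch between step 3's list of reasons and scenario 4 is a separate inconsistency in the text and does not depend on those assumptions.

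**What to change.** Leave the primary MMRM and the FAS tipping point as they are. In SAP 13.1.2.2 and the addendum:

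- Add a second run of scenario 4 on the Randomized Analysis Set, restricted to subjects with a baseline ABC-I. Say how never-dosed subjects are handled, since that set includes them.
- For subjects with no post-baseline ABC-I, apply delta to all post-baseline visits.
- Amend step 3 so that in scenario 4 delta applies to every dropout reason, including loss to follow-up and physician decision.

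If the placebo-based imputation of 13.1.2.1 is conducted, run it on the same wider population too, using the placebo model for all post-baseline visits of these subjects.

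The cost is SAP wording and one extra analysis, or two if the placebo-based imputation is done. Multiple imputation on the Randomized Analysis Set is already planned under 13.1.2.3, and eligibility requires a Baseline ABC-I score, so the covariate should be available. The downside is a possibly less favourable tipping point.

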4.5 Subject Discontinuation

Subjects may be discontinued from the study treatment for a number of reasons, including, but not limited to, those listed below:

- Adverse event.
- Death
- Lack of efficacy
- Lost to follow-up (Section 4.6)
- Non-compliance with study drug
- Physician decision
- Pregnancy
- Protocol deviation
- Study terminated by sponsor
- Use of prohibited medication
- Withdrawal of consent by subject (or by parent/LAR)
- Other

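### The tipping-point algorithm adds delta for one fixed list of dropout reasons, and that list matches none of the four scenarios the SAP sets out

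*SAP*

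**What the plan says.** SAP 13.1.2.2 commits to pattern-mixture sensitivity analyses under four scenarios for which dropouts count as MNAR:

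1. only subjects who left because of an adverse event
2. four named reasons, given as "Dropout reasons due to AE, lack of efficacy (LOE), COVID-19, use of prohibited medication as MNAR"
3. every dropout except those attributed to COVID-19
4. every dropout

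It then gives one five-step algorithm. Steps 1 and 2 impute under missing at random (MAR), steps 4 and 5 analyse and pool, and only step 3 departs from MAR. Step 3 reads "For subjects in the pimavanserin group with a dropout reason due to AE, LOE, subject withdraw consent, COVID-19, use of prohibited medication", and those subjects have delta added to all values after dropout. Nothing says that the list changes with the scenario.

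On the size and sign of delta, the section uses a percentage of the observed treatment difference for each dose comparison, and states "When delta > 0, the missing data are assumed to be MNAR". Section 2 of the SAP addendum removes the 100% cap and restates the grid as "in 5% increments of the observed treatment difference between a pimavanserin high dose and placebo" (and likewise for the low dose). It does not mention the scenarios, step 3 or the direction of the shift.

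Protocol 4.5 lists further discontinuation reasons that step 3 does not name, among them "Non-compliance with study drug", loss to follow-up, physician decision, protocol deviation and other.

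**The concern.** The scenarios and the algorithm cannot both be followed. Running four scenarios departs from step 3. Following step 3 gives one tipping value per dose comparison, on a set that the SAP never lists as a scenario, where the scenarios call for four. Protocol 9.1 requires deviations from the SAP to be described and justified in the study report, so either route leaves something to explain.

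The tipping value depends directly on which dropouts receive delta. A value computed on the step 3 list but reported as the AE-only, non-COVID or all-dropout scenario would describe a different missing-data assumption from its label.

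A secondary point is direction. Higher ABC-I is worse (SAP 5.2.1), so a benefit is negative when expressed as pimavanserin minus placebo. The SAP gives no order of subtraction and no absolute value. Adding a percentage of a negative difference would improve the imputed scores, and the result would never tip.

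**Working it through.** **Step 1: compare the lists.** The reasons are those in Protocol 4.5 plus COVID-19, which SAP section 6 counts as a discontinuation reason.

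| Scenario | In step 3 but not in the scenario | In the scenario but not in step 3 |
|---|---|---|
| 1 | lack of efficacy, withdrawn consent, COVID-19, prohibited medication | none |
| 2 | withdrawn consent | none |
| 3 | COVID-19 | death, loss to follow-up, non-compliance, physician decision, pregnancy, protocol deviation, sponsor termination, other |
| 4 | none | the same eight reasons |

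Exact matches: 0 of 4. Scenario 2 is the nearest.

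**Step 2: planning inputs (SAP 3.5).** Difference 5, SD 10, 64 evaluable per arm, two-sided 0.05, up to 15% discontinuation, 76 randomized per arm. These reproduce: t-test power is 80.1% at 64 per arm (79.5% at 63); 64/0.85 = 75.3, rounded up to 76; 3 × 76 = 228.

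**Step 3: how the tipping value depends on the list.** Let *k* pimavanserin dropouts out of 76 receive delta, and let *D* be the size of the observed benefit.

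- SE = 10 × √(2/64) = 1.768
- Smallest significant difference = t(0.975, 126) × 1.768 = 3.498
- Loss of benefit = (*k*/76) × delta
- Tipping delta, as % of *D* = 100 × (*D* − 3.498) / ((*k*/76) × *D*)

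The documents give no split by reason. Assume 11 dropouts in the arm (15% of 76 is 11.4), of which 3 are AE-only and 9 fall under the step 3 list.

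| Observed *D* | *k* = 3 (scenario 1) | *k* = 9 (step 3 list) | *k* = 11 (scenario 4) |
|---|---|---|---|
| 5.0 | 761% | 254% | 207% |
| 4.0 | 318% | 106% | 87% |
| 3.8 | 201% | 67% | 55% |

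For example, *D* = 5 and *k* = 9 gives 1.502 / (0.1184 × 5) = 2.54.

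The set tips at or before 100% when *D* < 3.498/(1 − *k*/76): below 3.64 for *k* = 3, 3.97 for *k* = 9 and 4.09 for *k* = 11.

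For scenario 2, if *w* of the 9 withdrew consent, the value rises by the factor 9/(9 − *w*). At *D* = 5 that is 1.502/((8/76) × 5) = 285% for *w* = 1, and 1.502/((6/76) × 5) = 380% for *w* = 3, against 254% on the step 3 list.

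**Step 4: allow for imputation variance.** The closed form ignores it. A simulation used six visits, 76 per arm, 11 monotone dropouts per arm, 40 imputations, Week 6 ANCOVA and Rubin's rules, with 60 significant trials per setting near each target *D*. Median tipping values for adjacent-visit correlation 0.6 / 0.8 were:

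| Observed *D* | *k* = 3 | *k* = 9 | *k* = 11 |
|---|---|---|---|
| 5.0 | 606 / 644% | 228 / 243% | 188 / 202% |
| 4.0 | 301 / 297% | 106 / 107% | 87 / 88% |
| 3.8 | 210 / 217% | 74 / 77% | 62 / 63% |

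At 3.8, the step 3 list tipped before 100% while AE-only did not in 50% / 60% of trials. With 60 trials the standard error of such a share is about √(0.5 × 0.5/60) = 6 percentage points.

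**Step 5: direction.** Shift 15% of the arm by 100% of a 5-point benefit. A worsening shift gives −5 + 0.15 × 5 = −4.25. The signed difference taken literally gives −5 + 0.15 × (−5) = −5.75.

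**The case against.** Read as a whole, the section calls for four scenarios, each of which already defines its own set. Step 3 looks like a template written for scenario 2 with one reason added, and a careful programmer would run all four. That is a plausible account of the intent, but the text does not say it, and the step that applies delta says something else.

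The sample code in Appendix 21.3 is not visible in the text available, and the version history says the sensitivity-analysis code was updated in version 3.0. It may settle both points, and this limit stands. Sample code marked as modifiable would still not remove a conflict in the governing prose.

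Direction can be inferred: delta is positive, it is added, higher scores are worse, and only worsening can overturn a favourable result. That is right, so direction is a clarification and not the main defect.

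The numbers rest on assumed values of *k*, and a spread across dropout sets is what the four scenarios are meant to display. The assumption is real. However, comparing *k* = 9 with *k* = 3 or 11 measures the error of reporting the step 3 result under the scenario 1 or 4 label. It is also true that at the planned effect every set tips near or above 190%, so only the reported figure moves. The reading at 100% changes only near the significance boundary, and 100% is a reading aid, not a rule in the plan.

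**Conclusion.** The point holds. Step 3 matches none of the four scenarios, the addendum leaves this unreconciled, and the direction of delta is implicit.

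The effect is on the reported tipping value and its label. Under the assumed split, the step 3 list gives about one third of the AE-only value (3/9 in the closed form) and about 1.2 times the all-dropout value (11/9). The gap from scenario 2 depends on how many subjects withdraw consent. For an observed difference near 3.8 to 4.0 points, the mismatch can decide whether the result survives dropouts losing the whole observed effect. At 5 points it does not.

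These sizes assume SD 10, 15% discontinuation and a split by reason that the documents do not supply. The matter is confined to one sensitivity analysis, although a firmly committed one that regulatory comments have already reopened. It should be corrected before unblinding; the primary MMRM, the testing order and the sample size are not touched.

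**What to change.** Replace step 3 with wording to this effect:

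> For pimavanserin subjects whose primary discontinuation reason is in the MNAR set of the scenario being run, add delta to each imputed ABC-I value after dropout. All other missing values remain imputed under MAR.

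Add a short table assigning every Protocol 4.5 reason, and COVID-19, to scenarios 1 to 4. It should state whether withdrawn consent belongs in scenario 2. Using the primary reason follows the convention already set in SAP 13.1.1 for classifying intercurrent events.

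Define delta as x% of the absolute LS mean difference for the dose comparison concerned, added as a positive amount that worsens ABC-I.

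Put this in the SAP addendum and confirm that the Appendix 21.3 code agrees. The cost is two sentences, one small table and a code check. No new data are needed.
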